### **7.3 ADHERENCE TO PROTOCOL**

The PI and the site staff shall strictly adhere to the protocol and GCP guidelines. All patients will be strictly required to follow the instructions given to them as per this protocol. For any deviation or violation from protocol, considered serious, the patient may be withdrawn from the study at the discretion of the Sponsor or the PI.

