#### 4.4 SUBJECT WITHDRAWAL

Subjects may withdraw from the study at any time for any reason without prejudice to his or her future medical care. Although a subject is not obliged to give his/her reason for withdrawing prematurely, the PI will make a reasonable effort to obtain the reason while fully respecting the subject's rights. If there is a medical reason for withdrawal, the subject will remain under the supervision of the PI for follow-up of AE(s) as detailed in *Section 9.4.3*. Every effort will be made to continue clinical and/or laboratory follow-up, as appropriate, in subjects who wish to withdraw from the study drug ) and reasonable efforts will be made to contact a subject who fails to attend any follow-up appointments, in order to ensure that he/she is in satisfactory health. A subject's withdrawal of consent and agreement to undergo a final examination will be documented on the case report form (CRF) and on the PI's copy of the ICF, which will be countersigned and dated by the subject.

As far as possible, all assessments scheduled for End-of-treatment must be performed on all subjects who receive the study drug but do not complete the study according to protocol. However, liver biopsy should be performed in those subjects who have completed at least 12 weeks of the study treatment.

	Approved by: [name] [name]	Protocol No.: SARO.17.004.02.PROTOCOL Version No.: 2.0
---	---	---

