#### 4.6 STOPPING CRITERIA FOR INDIVIDUAL PATIENTS

The following clinical events warrant discontinuation of study drug; however, the patient will continue to be followed for safety, liver function tests and lipid levels until the event has resolved, i.e., clinical laboratory value(s) has/have returned to baseline or is/are no longer of clinical significance. Discontinuation of study drug will only occur if mandated by safety events as defined below:

- Discontinue any patient with an adverse event of Common Terminology Criteria for Adverse Event (CTCAE) of grade 3 or higher that is possible or likely drug-related and discontinue any patient with an adverse event of CTCAE of grade 4 regardless of attribution to drug.
- Serious AE (SAE) that may be related to the drug and warrant discontinuation as per discretion of the PI;
- In the opinion of the PI, continuation of study drug poses a health risk to the patient.
- Evidence of drug induced liver injury requiring study drug discontinuation as shown in the algorithm below.
  - If patients with abnormal baseline liver indices develop elevations of AST or ALT greater than 2 times baseline or total bilirubin greater than 1.5 X baseline values while on study, testing should be repeated within 48-72 hours. If there are persistent elevations in ALT or AST greater than 2 X baseline or total bilirubin greater than 1.5 X baseline values, then close observation (see DILI Guidance for definition, testing and physical examination 2-3 times per week) should be initiated or drug should be discontinued.
  - A decision to discontinue or temporarily interrupt a study drug should be considered based on factors that include how much higher baseline ALT and AST were relative to the upper limit of normal (ULN) and how much the on study ALT

	Approved by: [name] [name]	Protocol No.: SARO.17.004.02.PROTOCOL Version No.: 2.0
--	------------------------------------	---

 Zydus Discovery DMCC	CLINICAL TRIAL PROTOCOL Saroglitazar Magnesium – Phase 2 SARO.17.004	CONFIDENTIAL Page 33 of 76
--	---	---

and AST levels have increased relative to baseline, in addition to whether there is concomitant elevation of bilirubin or INR.

- The criteria for discontinuing or temporarily interrupting study drug are as follows:
  - When the baseline values were  $\geq 1.5 \times \text{ULN}$  but  $< 5 \times \text{ULN}$ , discontinue if ALT or AST increases to  $> 3 \times$  baseline value

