### **7.5 PROTOCOL DEVIATIONS**

For the purpose of this study, no distinction will be made between Protocol Violations and Deviations. Deviations will be categorized as Clinical Study Report (CSR) non-reportable protocol deviations and as CSR reportable protocol deviations. A CSR non-reportable protocol deviation includes any deviations that do not necessarily influence the results/outcome of

 
Zydus Discovery DMCC
	
CLINICAL TRIAL PROTOCOL  Saroglitazar Magnesium – Phase 2  SARO.17.004
	
CONFIDENTIAL  Page 52 of 76

--	---	---

primary endpoints or patient safety. A CSR non-reportable protocol deviation does not require immediate notification to the IRB/IEC unless otherwise specified by IRB/IEC requirements. All CSR non-reportable protocol deviations will be noted in monitoring reports and provided to the PI by monitor, if required.

A CSR reportable protocol deviation includes any violation that may influence the results/outcome of primary endpoints or patient safety. CSR reportable protocol deviations must be reported immediately to the Regulatory, IRB/IEC, as specified by the regulatory requirements. All CSR reportable protocol deviations will also be reported to the Sponsor immediately. These deviations will also be noted in the monitoring reports and provided to the PI by monitor.

Note: Persistent non-compliance of CSR non-reportable protocol deviations may rise to the level of being considered CSR reportable protocol deviations (i.e., persistent non-compliance with dosing).

The Sponsor reserves the right to terminate the study at a given site in the event of monitoring and/or auditing findings of serious or persistent non-compliance with the protocol, SOPs, GCP and/or applicable regulatory requirement(s) by the PI/Institution. In all cases of site closure due to protocol deviations, the IRB/IEC and regulatory authorities will be informed.

The clinical study report will provide the list of protocol deviations in a separate section. The result will be analysed for all participants with CSR reportable protocol deviations.

Protocol deviations will include but are not limited to the following;

- Patients who did not meet entry criteria.
- Patients who received the wrong treatment or incorrect dose.
- Patients who received restricted medications.
- Failure to report within specified time lines of the planned visits.
- IP non-compliance of <80% or >120%.

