##### 8.2.1.3 Per-protocol population (PP)

The per-protocol population (PP) includes:

1. All enrolled patients who meet all the eligibility criteria.

	Approved by: [name] [name]	Protocol No.: SARO.17.004.02.PROTOCOL Version No.: 2.0
---	------------------------------------	---

 Zydus Discovery DMCC	CLINICAL TRIAL PROTOCOL Saroglitazar Magnesium – Phase 2 SARO.17.004	CONFIDENTIAL Page 55 of 76
--	---	---

2. Completed the study in compliance with the protocol.
3. Do not have any CSR reportable protocol deviation that affects the evaluation of the efficacy endpoints.

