3.1 Efficacy Analysis Populations

The modified intent-to-treat (mITT) population includes all randomized patients who receive at least one dose of study drug and have at least one post-baseline visit. The mITT population will serve as the primary population for all efficacy analyses. Last observation carried forward (LOCF) method will be used as an imputation method for the efficacy variables with missing observations.

The supportive analysis of the primary and secondary efficacy endpoints will be conducted using the per-protocol population (PP). The PP population includes all randomized patients who meet all eligibility criteria, completed the study in compliance with the protocol, and do not have any CSR reportable protocol deviation that affects the evaluation of the efficacy endpoints.

The number of patients excluded from mITT and PP populations and a listing of excluded subjects from each analysis population with reason for exclusion will be presented. Any inconsistencies in key study results between mITT and PP populations will be examined and discussed in the clinical study report.

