6.5 Sensitivity Analysis

A sensitivity analysis to explore the robustness of the efficacy results with respect to the protocol deviations will be performed using Per-Protocol population for the primary and secondary efficacy endpoints.

Statistical Analysis Plan			
Version Number:	1.0	Date:	31 Mar 2020
Protocol Number:	SARO.17.004	Sponsor Name:	Zydus Discovery DMCC

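### Protocol 7.3 allows a randomized patient to be withdrawn from the study for a serious deviation; the analysis does not need this, and it can cost primary-endpoint data in arms of 6, 6 and 3

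*Protocol*

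**What the plan says.** Protocol 7.3: "For any deviation or violation from protocol, considered serious, the patient may be withdrawn from the study at the discretion of the Sponsor". The same discretion is given to the PI. The rule is permissive, it concerns the study and not just study drug, and serious is not defined.

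Deviations are also dealt with elsewhere:
- Protocol 7.5 sorts them into reportable and non-reportable, according to whether they may influence the primary endpoint or patient safety, and adds: "The result will be analysed for all participants with CSR reportable protocol deviations".
- Protocol 8.2.1.3 makes this a condition of the PP set: "Do not have any CSR reportable protocol deviation that affects the evaluation of the efficacy endpoints".
- SAP 3.1: "The mITT population will serve as the primary population for all efficacy analyses". The mITT definition asks for one dose and one post-baseline visit and does not exclude deviators.
- SAP 6.5: "A sensitivity analysis to explore the robustness of the efficacy results with respect to the protocol deviations will be performed using Per-Protocol population".

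On leaving the study early, Protocol 4.4 asks for end-of-treatment assessments, as far as possible, in treated non-completers, and says that "liver biopsy should be performed in those subjects who have completed at least 12 weeks of the study treatment". Protocol 4.5 asks for continued clinical and laboratory follow-up of withdrawn subjects; deviation is not among its listed reasons for discontinuation. Protocol 4.6 says of study drug: "Discontinuation of study drug will only occur if mandated by safety events as defined below". Under SAP 6.8, LOCF uses post-baseline values only.

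**The concern.** The primary endpoint needs a second biopsy, and only one is scheduled on study, at Week 24. A deviation arises after randomization, and some of the kinds listed in Protocol 7.5, such as restricted medication or poor compliance, may depend on treatment or on response. If the response to a deviation is to remove the patient from the study, someone who could have supplied a Week 24 NAS to mITT, and been left out of PP only, may supply none or an early one. That is avoidable missing data for a post-randomization reason, decided under an undefined criterion, in a trial whose placebo arm has 3 patients. It also thins the comparison of mITT with PP, which is how the SAP proposes to judge robustness to deviations.

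**Working it through.** **1. What withdrawal changes.** Take a patient with a reportable deviation that affects efficacy and at least one post-baseline visit.

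| Course | NAS in mITT | In PP |
|---|---|---|
| Stays in follow-up, biopsied at Week 24 | Week 24 value | No (8.2.1.3) |
| Withdrawn before 12 weeks of treatment | None: 4.4 calls for no biopsy, and SAP 6.8 does not carry baseline forward | No (8.2.1.3, 8.2.6) |
| Withdrawn at 12 weeks or later | Early value if the biopsy is done, as early as half the planned exposure (12/24) | No (8.2.1.3, 8.2.6) |

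PP membership is the same in all three rows. Withdrawal changes only the mITT column, and for NAS it moves that set towards PP.

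**2. Sample size.** Protocol 8.4 gives 15 patients at 2:2:1. 15 × 2/5 = 6, 15 × 2/5 = 6, 15 × 1/5 = 3, which reproduces the stated 6/6/3. SAP section 4 says no formal sample size estimation was done, so there is no power figure to reproduce.

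**3. Share of an arm.** One lost NAS is 1/3 = 33% of placebo or 1/6 = 17% of an active arm.

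**4. Precision.** SAP 6.4 promises 95% confidence intervals for treatment differences. Assuming a two-sample t interval with common SD, the half-width in SD units is t(0.975, n1 + n2 − 2) × √(1/n1 + 1/n2).
- 6 vs 3: SE 0.707 SD, half-width 1.67 SD.
- 6 vs 2 (one placebo NAS lost): SE 0.816 SD, half-width 2.00 SD, which is 1.998/1.672 = 1.195, or 19.5% wider.
- 5 vs 3 (one active NAS lost): SE 0.730 SD, half-width 1.79 SD, about 7% wider.

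The responder endpoints come from the same biopsy. The smallest two-sided Fisher p-value attainable is 1/84 = 0.0119 at 6 vs 3 and 1/28 = 0.0357 at 6 vs 2.

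**5. Worst-case bounds.** By Protocol Appendix 2, NAS runs from 0 to 3 + 3 + 2 = 8. A missing Week 24 score can therefore vary over 8 points whatever the baseline, and one missing value leaves the arm's mean change undetermined over 8/3 = 2.67 points (placebo) or 8/6 = 1.33 points (active).

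**6. How often.** The documents give no rate. Assume that each patient is independently withdrawn for a deviation with probability q. The chance of at least one among the 3 placebo patients is 1 − (1 − q)³:
- q = 5%: 1 − 0.95³ = 14%.
- q = 10%: 1 − 0.90³ = 27%.

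At those rates, these are upper bounds on the chance of losing a placebo NAS through this rule, because a withdrawal after 12 weeks may still yield a biopsy.

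**The case against.** A reader might infer more than the documents support, in four ways.

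- **That primary-endpoint data are necessarily lost.** The rule is discretionary and confined to deviations judged serious. Protocol 4.4 calls for a biopsy after at least 12 weeks of treatment, and LOCF could carry that NAS. Protocol 4.5 continues clinical and laboratory follow-up, so withdrawal does not plainly end all contact. This stands. What remains is the gap before 12 weeks, the early value after it, and the fact that 4.5 does not mention biopsy.
- **That the mITT/PP comparison is defeated.** A patient with an efficacy-affecting reportable deviation leaves PP either way, and laboratory values stay in mITT through LOCF. The comparison is weakened for NAS only.
- **That 7.3 flatly contradicts 4.6.** Section 4.6 governs study drug and 7.3 governs participation; 4.5 already contains non-safety exits, and its list is not said to be exhaustive. This is an inconsistency to reconcile. Section 5.10 on treatment compliance appears in the contents, but its text is not in the copy available, so the handling of non-compliance is not fully visible.
- **That a lost NAS is more likely than not.** At the same assumed rates, the chance of any withdrawal among 15 is 1 − 0.95¹⁵ = 54% to 1 − 0.90¹⁵ = 79%. That counts withdrawals, not lost scores.

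Two further points are fair. Listed deviations include unmet entry criteria and wrong treatment or dose, and some reportable deviations concern safety, so a discretionary exit may have a purpose outside the analysis. Blinding under SAP 2.4 also limits deliberate selective withdrawal, although a deviation can still depend on treatment. Neither point requires that a deviation by itself end data collection.

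**Conclusion.** The concern holds in a limited form. Protocol 7.3 allows withdrawal from the study for an undefined class of deviations, the analysis gains nothing from it, and it sits awkwardly with the statement in 7.5 that results from reportable deviators will be analysed. NAS data can be lost outright before 12 weeks of treatment and displaced to an earlier time after that. The size is one third of the placebo arm per lost score and a half-width of 2.00 instead of 1.67 SD. How often this would occur is unknown; the 14% to 27% figure rests on an assumed rate of 5% to 10%. With no formal hypothesis testing and no power target, the consequence is less precise and possibly biased descriptive estimates, not a power shortfall. The change is worth making mainly because it is cheap.

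**What to change.** Amend Protocol 7.3 to say that a protocol deviation alone does not end study follow-up. The deviation is recorded and categorised under 7.5 and handled through PP exclusion. The patient remains in mITT and continues the assessments already scheduled, with the planned Week 24 biopsy offered, unless consent is withdrawn or follow-up is judged unsafe.

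Reconcile 7.3 with 4.4 (the 12-week condition for biopsy), 4.5 and 4.6, including on whether a deviation can end study drug. No clinical rule is proposed here; that choice belongs to the sponsor and investigators.

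The cost is a wording amendment, since the visits and the biopsy are already scheduled for every patient. The small downside is that non-adherent patients stay in the mITT estimate, which the mITT definition already allows.

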### **7.4 DATA MONITORING COMMITTEE**

Safety data will be reviewed regularly by a Data Monitoring Committee (DMC). The Data Monitoring Committee comprised of an unblinded independent statistician and hepatologist who will review periodic reports from the EDC. The formal structure and conduct of DMC will be according to a previously agreed upon remit.

### **7.5 PROTOCOL DEVIATIONS**

For the purpose of this study, no distinction will be made between Protocol Violations and Deviations. Deviations will be categorized as Clinical Study Report (CSR) non-reportable protocol deviations and as CSR reportable protocol deviations. A CSR non-reportable protocol deviation includes any deviations that do not necessarily influence the results/outcome of

 
Zydus Discovery DMCC
	
CLINICAL TRIAL PROTOCOL  Saroglitazar Magnesium – Phase 2  SARO.17.004
	
CONFIDENTIAL  Page 52 of 76

--	---	---

primary endpoints or patient safety. A CSR non-reportable protocol deviation does not require immediate notification to the IRB/IEC unless otherwise specified by IRB/IEC requirements. All CSR non-reportable protocol deviations will be noted in monitoring reports and provided to the PI by monitor, if required.

A CSR reportable protocol deviation includes any violation that may influence the results/outcome of primary endpoints or patient safety. CSR reportable protocol deviations must be reported immediately to the Regulatory, IRB/IEC, as specified by the regulatory requirements. All CSR reportable protocol deviations will also be reported to the Sponsor immediately. These deviations will also be noted in the monitoring reports and provided to the PI by monitor.

Note: Persistent non-compliance of CSR non-reportable protocol deviations may rise to the level of being considered CSR reportable protocol deviations (i.e., persistent non-compliance with dosing).

The Sponsor reserves the right to terminate the study at a given site in the event of monitoring and/or auditing findings of serious or persistent non-compliance with the protocol, SOPs, GCP and/or applicable regulatory requirement(s) by the PI/Institution. In all cases of site closure due to protocol deviations, the IRB/IEC and regulatory authorities will be informed.

The clinical study report will provide the list of protocol deviations in a separate section. The result will be analysed for all participants with CSR reportable protocol deviations.

Protocol deviations will include but are not limited to the following;

- Patients who did not meet entry criteria.
- Patients who received the wrong treatment or incorrect dose.
- Patients who received restricted medications.
- Failure to report within specified time lines of the planned visits.
- IP non-compliance of <80% or >120%.

## 7.6 ADJUDICATION

[figure not shown]
An external independent Central Adjudication Committee (CAC) will adjudicate serious adverse events (SAEs), including all deaths, that are known or suspected to be a Major Adverse Cardiac Events (MACE) or heart failure hospitalizations. The CAC members will be independent of the

	
Approved by: [name] [name]
	
Protocol No.: SARO.17.004.02.PROTOCOL Version No.: 2.0

--	---	--

 Zydus Discovery DMCC	CLINICAL TRIAL PROTOCOL Saroglitazar Magnesium – Phase 2 SARO.17.004	CONFIDENTIAL Page 53 of 76
--	---	---------------------------------------

Sponsor, the clinical study sites and Investigators. The blinded medical review of known or suspected MACE will primarily focus on CV death, myocardial infarction, cerebrovascular accident (stroke) and hospitalization for heart failure.

A detailed CAC Charter and adjudication process will be described in a separate document.

	Approved by: [name] [name]	Protocol No.: SARO.17.004.02.PROTOCOL Version No.: 2.0
---	------------------------------------	---

 Zydus Discovery DMCC	CLINICAL TRIAL PROTOCOL Saroglitazar Magnesium – Phase 2 SARO.17.004	CONFIDENTIAL Page 54 of 76
--	---	---

## 8 BIOSTATISTICS

### 8.1 STATISTICAL DESIGN

Statistical analysis will be performed on efficacy variables.

As this is a proof of concept (PoC) study no formal hypothesis testing will be done. All primary and secondary efficacy analysis will be summarised and analysed, appropriately, for modified Intent-To-Treat (mITT) and Per Protocol (PP) populations. The PP population will consist of all randomized patients completing the treatment phase (has taken  $\geq 80\%$  and  $\leq 120\%$  of the study drug) as per the study protocol and do not have any CSR reportable protocol deviation in such a way that could affect efficacy outcome. The mITT population will consist of all randomized patients who have taken at least one dose of the study treatment and have at least one post-baseline efficacy data. Last observation carried forward method will be used as an imputation method for post-baseline missing values for mITT analysis.

### 8.2 PLANNED ANALYSIS

#### 8.2.1 Populations

##### 8.2.1.1 Safety population

The safety population includes all enrolled patients who received at least single dose of IP.

##### 8.2.1.2 Modified intention-to-treat population (mITT)

The modified intent-to-treat (mITT) population includes:

1. All enrolled patients who received at least one dose of the IP.
2. Appear for at least one post baseline visit.

All primary and secondary objectives will be analyzed using mITT population with post-baseline LOCF method. Last observation carried forward (LOCF) method will be used as an imputation method for post-baseline missing values.

##### 8.2.1.3 Per-protocol population (PP)

The per-protocol population (PP) includes:

1. All enrolled patients who meet all the eligibility criteria.

	Approved by: [name] [name]	Protocol No.: SARO.17.004.02.PROTOCOL Version No.: 2.0
---	------------------------------------	---

 Zydus Discovery DMCC	CLINICAL TRIAL PROTOCOL Saroglitazar Magnesium – Phase 2 SARO.17.004	CONFIDENTIAL Page 55 of 76
--	---	---

2. Completed the study in compliance with the protocol.
3. Do not have any CSR reportable protocol deviation that affects the evaluation of the efficacy endpoints.

### 8.2.2 Statistical Analysis

As this is a proof of concept (PoC) study no formal hypothesis testing will be done.

All primary and secondary efficacy analysis will be summarised and analysed, appropriately, for modified Intent-To-Treat (mITT) and Per Protocol (PP) populations.

Change and percentage change for primary and secondary efficacy endpoints (continuous data) will be calculated as follows:

Change from baseline to Week 24 will be determined as (Week 24 - Baseline) and

[figure not shown]
Percentage change from baseline will be determined as  $[(\text{Week 24} - \text{Baseline})/\text{Baseline}] * 100$ .

All primary and secondary endpoints will be summarized as: n, mean, standard deviation, median, minimum and maximum for continuous variables; count and percentage for categorical variables at each visit.

